9.5 Study Assessments

9.5.1 Assessments

9.5.1.1 Demography

Subject demography information will be collected at the Screening Visit. Demography information includes date of birth (or age), sex, and race/ethnicity.

9.5.1.2 Pretreatment/Screening Assessments

Baseline characteristics and assessments will be collected during the Pretreatment Phase/Screening Period, which will last from -21 days to -1 day before the Treatment Phase begins. All Pretreatment and Screening assessments are listed in the Schedule of Procedures/Assessments ([Table 8](#)).

Medical/Surgical History and Physical Examination

Medical and surgical history and current medical conditions will be recorded at the Screening Visit. Significant findings prior to the start of study drug will be recorded on the Medical History and Current Medical Conditions CRF.

Physical examinations (comprehensive or symptom directed) will be performed as designated in the Schedule of Procedures/Assessments ([Table 8](#)). A physical examination will include evaluations of the head, eyes, ears, nose, throat, neck, chest (including heart and lungs), abdomen, limbs, skin, and a complete neurological examination. A urogenital examination will be required only in the presence of clinical symptoms related to this region.

Documentation of the physical examination will be included in the source documentation at the site. Significant findings at the Screening Visit will be recorded on the Medical History and Current Medical Conditions CRF. Changes during treatment from the screening physical examination findings that meet the definition of an AE will be recorded on the Adverse Events CRF.

Pregnancy Test

A serum (a 6-mL sample of blood will be collected) or urine beta-human chorionic gonadotropin (β -hCG) test will be performed for premenopausal women and postmenopausal women who have been amenorrheic for less than 12 months. Please refer to the Schedule of Procedures/Assessments ([Table 8](#)).

Electrocardiogram (ECG)

Electrocardiograms will be obtained at Screening as designated in the Schedule of Procedures/Assessments ([Table 8](#)). Complete, standardized, 12-lead ECG recordings that permit all 12 leads to be displayed on a single page with an accompanying lead II rhythm strip below the customary 3×4 lead format are to be used. In addition to a rhythm strip, a

minimum of 3 full complexes should be recorded from each lead simultaneously. Subjects must be in the recumbent position for a period of 5 minutes prior to the ECG.

An ECG abnormality may meet the criteria of an AE as described in this protocol (see [Section 9.5.1.6.1](#)) and the CRF Completion Guidelines. In these instances, the AE corresponding to the ECG abnormality will be recorded on the Adverse Events CRF.

Other assessments

Additional Screening assessments will include safety laboratory assessments, vital signs, ECOG, mTNBC diagnosis, TNM staging at diagnosis ([Appendix 8](#)), prior anticancer therapy, and tumor tissue for PD-L1 expression.

9.5.1.3 Treatment/End of Treatment Assessments

Treatment and End of Treatment assessments are listed in the Schedule of Procedures/Assessments ([Table 8](#)).

Dose-limiting toxicity (DLT) assessments will be conducted for Phase 1b subjects. A DLT is defined as one of the following toxicities occurring during the DLT assessment window and considered by the investigator to be related to either of the study drugs.

Hematologic Toxicities:

- Any Grade 4 thrombocytopenia or neutropenia lasting >7 days

Nonhematologic Toxicities:

- Episcleritis, uveitis, or iritis of Grade 2 or higher
- Any Grade 4 toxicity
- Any Grade 3 toxicity EXCLUDING:
 - Nausea/vomiting/diarrhea controlled by medical intervention within 72 hours
 - Grade 3 rash in the absence of desquamation, no mucosal involvement, does not require steroids, and resolves to Grade 1 by the next scheduled dose of pembrolizumab
 - Transient Grade 3 AST or ALT elevation, defined as no more than 3 days with or without steroid use
- Discontinuation or delay of more than 2 weeks of either study medication due to treatment-related AE will be considered as a DLT

All subjects enrolled in Phase 1b will be assessed for DLTs during a DLT assessment window of the first cycle of 21 days. Subjects who discontinue study treatment prior to completing the DLT assessment window for any reason other than a DLT will be replaced.

End of Treatment assessments for all subjects will be collected within 30 days of the last dose of study drug. Subjects with SAEs and/or ECIs at the time of End of Treatment will be followed for 90 days after the last dose of study drug or, if the subject initiates new anticancer therapy, for 30 days following the last dose of study drug, whichever is earlier.

9.5.1.4 Efficacy Assessments

Tumor response data utilized in the main analysis of ORR, PFS and DOR will be obtained from an independent review of the imaging scans. In addition, these analyses will be performed using the investigators' determination of tumor response, which will be considered secondary. Detailed methodology for assessment by independent review will be provided in an Independent Imaging Review Charter. Secondary endpoint OS will be assessed throughout the study.

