A brain scan (CT with contrast or MRI pre- and post-gadolinium) must be performed at Screening (within 28 days prior to Cycle 1/Day 1), to assess potential CNS disease and/or metastases. For subjects with previously treated eligible brain metastases, a brain scan will be performed at tumor assessment time points, if clinically indicated.

The tumor assessment schedule should not be affected by interruptions in study treatment.

The same method of assessment used at Screening must be used at all time points.

Throughout the study it is critical that the same imaging methodology be applied and contrast be consistently provided unless IV contrast becomes medically contraindicated during the course of treatment or the dose of contrast needs to be adjusted based on the subject's health status.

Bone scans will be performed at Screening, every 27 weeks, or sooner if clinically indicated, and at confirmation of CR. A bone scan (⁹⁹m-technetium polyphosphonate scintigraphy, whole body bone MRI, or ¹⁸F-NaF-PET) to assess bone metastases will be performed within 6 weeks prior to C1D1 (historical scans are acceptable) and then every 27 weeks (within that 27th week) from C1D1, or sooner if clinically indicated. In subjects whose body CT/MRI scans indicate CR has been achieved, a bone scan will be required at confirmation of CR to exclude new bone metastases. The same methodology and acquisition techniques used at screening should be used throughout the study to ensure comparability. Lesions detected on bone scans must be followed with cross-sectional imaging.

Tumor response will be confirmed by a second examination performed no less than 4 weeks after the first observation of response. Best overall response (BOR) of stable disease requires at least 1 posttreatment assessment that meets the SD criteria at least 8 weeks after the start of treatment.

In subjects who discontinue study therapy without documented disease progression, every effort should be made to continue monitoring their disease status by radiologic imaging every 9 weeks \pm 1 week during Year 1, and every 9 to 12 weeks \pm 1 week thereafter according to standard of care, until (1) the start of new anticancer treatment, (2) disease progression (3) death, or (4) the end of the study, whichever occurs first.

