9.5.1.4.2 IRRECIST AFTER INITIAL RADIOLOGIC PROGRESSION

Since pembrolizumab, like other immunotherapeutic agents, may produce antitumor effects after an initial increase in tumor burden, standard RECIST criteria may not provide a complete response assessment of its efficacy. irRECIST is RECIST 1.1 adapted as described below to account for the unique tumor response seen with immunotherapeutic drugs. irRECIST will be used by site investigator/local radiology review to assess tumor response and progression, and make treatment decisions. This data will be collected in the clinical database. Treatment efficacy based on irRECIST as assessed by central imaging vendor review will be evaluated retrospectively.

The key changes for irRECIST from RECIST v1.1 is the ability to continue treatment, if clinically stable, until a repeat imaging scan \geq 4 weeks after the first radiologic evidence of PD confirms progressive disease. Therefore, in addition to radiographic assessment of tumor response or progression, irRECIST (see [Appendix 4](#)) takes into account the clinical condition/stability of subjects ([Table 6](#)).

Clinically stable is defined by the following criteria:

- Absence of signs and symptoms (including worsening of laboratory values) indicating disease progression
- No decline in ECOG performance status
- Absence of rapid progression of disease
- Absence of progressive tumor(s) at critical anatomical sites (eg, cord compression) requiring urgent alternative medical intervention
- No requirements for intensified management, including increased analgesia, radiation, or other palliative care

Table 6 Imaging and Treatment After First Radiologic Evidence of Progressive Disease

	Clinically Stable		Clinically Unstable	
	Imaging	Treatment	Imaging	Treatment
1 st radiologic evidence of PD by RECIST 1.1	Repeat imaging at ≥ 4 weeks at site to confirm PD	May continue study treatment at the local site investigator's discretion while awaiting confirmatory tumor imaging by site by irRECIST	Repeat imaging at ≥ 4 weeks to confirm PD per physician discretion only	Discontinue treatment
Repeat tumor imaging confirms PD by irRECIST at the local site	No additional imaging required	Discontinue treatment (exception is possible upon consultation with sponsor)	No additional imaging required	N/A

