Repeat tumor imaging shows SD, PR or CR by irRECIST by the local site	Continue regularly scheduled imaging assessments	Continue study treatment at the local site investigator's discretion	Continue regularly scheduled imaging assessments	May restart study treatment if condition has improved and/or clinically stable per investigator's discretion. Next tumor image should occur according to the every 9 weeks (± 1 week) imaging schedule

CR = complete response. N/A = not applicable, PD = progressive disease, PR = partial response, SD = stable disease.

- In determining whether or not the tumor burden has increased or decreased, local study site investigators should consider all target lesions as well as non-target lesions. Subjects that are deemed clinically unstable are not required to have repeat tumor imaging for confirmation.
- For a **clinically stable** subject with first radiologic evidence of progressive disease by RECIST 1.1 (ie, **unconfirmed progression of disease**), it is at the discretion of the

site investigator to continue treating the subject with the assigned treatment per protocol until progression of disease is confirmed at least 28 days from the date of the scan first suggesting PD. If radiologic progression is confirmed by subsequent scan then the subject will be discontinued from study treatment. If radiologic progression is not confirmed by irRECIST per the site, then the subjects may continue on treatment and follow the regular imaging schedule intervals until progression is confirmed at a later time point by the site.

- **NOTE:** If a subject has confirmed radiographic progression (ie, 2 scans at least 4 weeks apart demonstrating progressive disease) per irRECIST, but the subject is achieving a clinically meaningful benefit, and there is no further increase in the tumor burden at the confirmatory tumor imaging, an exception to continue treatment may be considered following consultation with the sponsor. In this case, if treatment is continued, tumor imaging should continue to be performed following the intervals as outlined in sections 6.0 Study Flowchart and be submitted to the central imaging vendor. Note: As of Protocol Amendment 05, tumor assessment scans will no longer be sent to the central imaging laboratory.
- Any subject deemed **clinically unstable** should be discontinued from study treatment at 1st radiologic evidence of PD and is not required to have repeat imaging for PD confirmation.

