Censoring rule for PFS by RECIST 1.1

The PFS derivation rules in this SAP follow the sensitivity of analyses described in Food and Drug Administration (FDA) “[Guidance for Industry Clinical Trial Endpoints for the Approval of Cancer Drugs and Biologics \(2007\)](#)”.

Definition of Progression Date: Progression date is assigned to the first time at which radiological progression can be declared.

For progression based on a new lesion, the progression date is the date of the initial detection of the new lesion, if there were multiple new lesions detected, then the earliest date of initial detection will be used.

Table 3 shows the primary censoring rules for the derivation of PFS based upon investigator's tumor assessment.

Censoring rule for irPFS by irRECIST

Definition of progression date by irRECIST (i.e., irPD):

- For the subjects who experience PD by RECIST 1.1 and then confirmed by irPD ($>$ or <28 days) or not confirmed due to any reasons, the first documented PD date by RECIST 1.1 is the date of irPD.
- For the subjects who experience PD by RECIST1.1 and then followed by irCR/irPR/irSD, the first documented progression date is the date of first irPD defined by irRECIST.
- If the subject had new lesion earlier than overall timepoint response of PD in irRECIST, the date of new lesion is not counted as irPD date. (this is different from PD by RECIST 1.1 for which, as soon as subject developed new lesions, subject is considered as PD and PD date is the date of new lesion).

Censoring rule will be same as RECIST1.1 except that for the second rule in [Table 3](#).

“Date of first radiologic PD assessment” means the irPD Date determined as above.

Duration of Response

Duration of Response (DOR) – defined as the time from the date that a confirmed objective response is first documented to the date of PD or death due to any cause for those subjects with a confirmed PR or CR. For subjects who did not experience PD or death by the end of data cut off, the date of last adequate radiologic assessment before missing tumor assessments or new anti-cancer therapy will be used as censoring date.

BOR, PFS and DOR will be defined separately for IIR data and for investigator reviewed data following the same rules.

Table 3. Censoring Rules for Analysis of Progression-Free Survival

No.	Situation	Date of Progression or Censoring	Outcome
1	No baseline or post-baseline tumor assessments	Date of the first dose	Censored

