2	Progression documented between scheduled visits	Date of first radiologic PD assessment	Progressed
3	No progression at the time of data cut-off	Date of last adequate radiologic assessment prior to or on date of data cut-off	Censored
4	New anticancer treatment started	Date of last adequate radiologic assessment prior to or on date of new anticancer treatment	Censored
5	Death before first PD assessment	Date of death	Progressed
6	Death between adequate assessment visits*	Date of death	Progressed
7	Death or progression after two or more missed visit**	Date of last adequate radiologic assessment before missed tumor assessments	Censored

CR = complete response, PD = progressive disease, PR = partial response, SD = stable disease,

* Adequate tumor assessment is a radiologic assessment of CR, PR, SD, non-CR/non-PD or PD as determined by investigators.

New anticancer treatment includes palliative radiotherapy. Any tumor assessments after new anticancer treatment started will be removed in the definition of PFS.

** More than two missed visits is defined if the duration between the last tumor assessment (including NE) and death or PD is longer than 126 days (18 weeks) or 168 days (e.g. 24 weeks) for subjects on the every 9 or 12 week scanning schedule in this study:

The priority of the censoring rules is as follows:

1. If the subject had PD or death, the following sequence will be applied:

- If a subject did not have baseline tumor assessment (No. 1), the subject will be censored on date of the first dose. However, if the subject did not have baseline tumor assessment and died within 126 days (18 weeks) after the first dose and did not receive new anticancer treatment, the date of death will be the PFS event date (not censored).
- If a subject had new anticancer treatment before PD or death (No. 4), the subject will be censored on the date of the last adequate tumor assessment prior to or on the date of new anticancer treatment.
- If a subject missed two assessments before PD or death (No. 7), the subject will be censored on the date of the last adequate tumor assessment before PD or death. Note that if a subject is censored by both this criterion and the anticancer treatment criteria, the earliest

censoring date will be used.

- Otherwise, if a subject had an event (No. 2, No. 5, or No. 6), the earliest event date will be used.

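### Independent review reads the main PFS and DOR, but required scans end on the site's progression call, so a progression seen only by the site is generally censored; separately, SAP Table 3 names the investigator as reader

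*Protocol*

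**What the plan says.** **Reader of the main analysis.** Protocol 9.5.1.4: "Tumor response data utilized in the main analysis of ORR, PFS and DOR will be obtained from an independent review of the imaging scans". SAP 6.1 agrees. Investigator-read PFS and DOR are planned as secondary or sensitivity analyses (Protocol 8.2 and 9.5.1.4; SAP 6.4.3).

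**Reader who controls treatment and imaging.** Protocol 9.5.1.4.2: "irRECIST will be used by site investigator/local radiology review to assess tumor response and progression, and make treatment decisions". In Table 6, a clinically stable subject with first progression has a further scan: "Repeat imaging at ≥ 4 weeks at site to confirm PD". Once the site confirms progression, the entry is "No additional imaging required", and the text adds "If radiologic progression is confirmed by subsequent scan then the subject will be discontinued from study treatment". A clinically unstable subject stops treatment at first progression and need not be rescanned. After treatment stops without documented progression, imaging continues "until (1) the start of new anticancer treatment, (2) disease progression (3) death, or (4) the end of the study, whichever occurs first" (Protocol 9.5.1.4.1). No reader is named there.

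**Censoring rules.** SAP Section 8: "Table 3 shows the primary censoring rules for the derivation of PFS"; the sentence goes on to give the investigator's assessment as the basis. The footnote reads: "Adequate tumor assessment is a radiologic assessment of CR, PR, SD, non-CR/non-PD or PD as determined by investigators". The same section states that response, PFS and DOR are derived once per reader, under identical rules.

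**The concern.** The reader whose progression call counts as the event in the main analysis is not the reader whose call ends the scans. When the two disagree, the IIR may never receive the scan on which it would have called progression. Kaplan-Meier estimation assumes that a censored subject has the same outlook as those still followed. A subject the site has just judged to be progressing probably has a worse one.

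The trial has one arm, so no control arm shares the bias. PFS and DOR probabilities at 12 months are planned outputs (Protocol 9.7.1.6.2; SAP 6.4.2), and Protocol 7.1 frames the aim as better efficacy than either drug alone, with the monotherapy PFS medians listed in Protocol Table 1.

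**Working it through.** **Step 1: path of a subject with site progression that the IIR does not call**

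- Clinically stable: one further scan at least 4 weeks later. If progression is not confirmed, scanning continues. If it is confirmed, no more imaging is required, except where treatment continues by agreement with the sponsor.
- Clinically unstable: imaging may end at the first site progression.
- In IIR PFS the subject is then censored at the last adequate assessment by Table 3 rule 3 (no progression at cut-off), rule 4 (new therapy) or rule 7 (death or progression after too long a gap).
- Exception: under rules 5 and 6 a death inside the gap limit, without earlier new therapy, is an event.
- In IIR DOR the censoring date is likewise the last adequate assessment before missing scans or new therapy.

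The only plan figures to check here are the gap limits: 2 × 9 × 7 = 126 days and 2 × 12 × 7 = 168 days. Both reproduce. The documents give no power, event count or precision for PFS or DOR, and no discordance rate.

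**Step 2: direction**

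Assume that the IIR would have called a discordant progression on average 1.5 scans later. Its chance of being called at each further scan is then 1/1.5 = 0.67. For subjects in general, the chance of progression per 9-week interval is 1 − exp(−ln2 × 63/median): 0.39 for a median of 87 days and 0.31 for 120 days. Censoring removes the higher-risk group, so the curve is too high. If discordant subjects had the same risk as the rest, there would be no bias.

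**Step 3: size, by Kaplan-Meier simulation (200,000 subjects per scenario)**

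- True progression: exponential, median 87 days (eribulin in Study 301, the highest PFS median in Protocol Table 1) or 120 days (assumed).
- Scans every 9 weeks ± 1 week (Protocol 9.5.1.4.1).
- Share q of site progressions not called by the IIR: 10% to 40% (assumed). The IIR is never ahead of the site.
- Comparator: scanning continued until IIR progression.
- Scenario A: scans stop at first site progression, no deaths.
- Scenario B: half of discordant subjects have one more scan 9 weeks later, and 15% of those still without an event die within 126 days.

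12-month PFS in %, as plan / continued scanning / excess in points:

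| True median | q | Scenario A | Scenario B |
|---|---|---|---|
| 87 d | 10% | 10.4 / 9.1 / +1.3 | 9.9 / 9.3 / +0.6 |
| 87 d | 20% | 13.6 / 10.4 / +3.2 | 11.7 / 10.4 / +1.3 |
| 87 d | 30% | 17.5 / 11.5 / +6.0 | 13.7 / 11.4 / +2.3 |
| 87 d | 40% | 22.4 / 12.5 / +9.9 | 16.1 / 12.6 / +3.5 |
| 120 d | 10% | 19.5 / 17.5 / +2.0 | 18.5 / 17.6 / +0.9 |
| 120 d | 20% | 23.4 / 18.9 / +4.5 | 20.8 / 18.8 / +2.0 |
| 120 d | 30% | 28.0 / 20.1 / +7.9 | 23.7 / 20.3 / +3.4 |
| 120 d | 40% | 34.1 / 21.8 / +12.3 | 26.4 / 21.5 / +4.9 |

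Median PFS rises by 0 to 5 days in A, except 248 against 191 days at 120 days and q = 40%, and by 0 to 2 days in B. Six-month PFS moves by +0.3 to +4.3 points in A and −0.3 to +0.6 points in B. DOR was not simulated; the same mechanism applies, but no figure is given.

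**Step 4: the Table 3 wording, a separate matter**

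Take a subject read as stable by both readers at Week 18. At Week 27 the investigator gives a reading, the IIR finds the scan not evaluable, and new therapy starts. Under the footnote as written, Week 27 is adequate because the investigator read it, so it sets the IIR censoring date. By the IIR's own reading the date would be Week 18. The difference is (27 − 18) × 7 = 63 days.

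**The case against.** The case on the other side is substantial.

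- *Stable subjects are rescanned, and early deaths count.* Correct. It would be wrong to say that scanning stops at the site's first call for everyone, or that every such subject is censored. Scenario B shows how far these features shrink the effect.
- *SAP Section 8 already applies the rules to each reader separately.* Correct as to intent. A reader might infer that the investigator wording in Table 3 causes the censoring. It does not: applied literally to investigator progression, the table would make these subjects events. The wording is its own defect, confined to which scan counts as adequate.
- *Investigator-read PFS is planned.* It covers much of the PFS question. It does not isolate discordant censoring, and investigator-read DOR uses a different responder set, so it cannot test IIR DOR.
- *PFS and DOR are descriptive.* Correct. The prespecified historical comparisons concern ORR only, so no formal claim turns on this point.
- *The Imaging Charter might provide for verification of progression.* Possible. It is not among the documents, and neither the protocol nor the SAP mentions such a step.

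A larger effect is also tempting. With the per-interval hazard h cut to h(1 − d), where d is the share of site progressions the IIR does not call, PFS after the Week 18 scan is (1 − h(1 − d))². For a true median of 87 days this rises from 36.6% at d = 0 to 46.8% at d = 20%. But that comparison takes the site's reading as the truth, so part of the gap is legitimate reader difference. It also leaves out confirmatory scans and early deaths. The documents do not support it as a measure of bias, nor the idea that PFS is overstated by the discordance rate itself.

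**Conclusion.** The point holds in a limited form. In the IIR analysis, a progression seen only by the site is generally censored, the censoring is informative, and the expected direction is upward for late PFS and DOR. The illustrative excess in 12-month PFS is 0.6 to 4.9 points with some confirmatory scans and early deaths, and 1.3 to 12.3 points if scans stop at first site progression. The median hardly moves, except at 40% discordance with the longer true median and no further scans.

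These sizes rest on the assumed discordance rate, the assumed 1.5-scan lag and exponential progression. The bias in this trial is expected, not demonstrated. The Table 3 wording needs correction whatever the discordance rate.

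**What to change.** 1. In SAP Table 3, its introduction and its footnote, define progression and adequate assessment by the reader whose data are analysed: the IIR for the main analysis, the investigator for the secondary one.
2. Tabulate the subjects censored in IIR PFS and in IIR DOR after an investigator progression.
3. Add a sensitivity analysis on IIR data in which an investigator RECIST 1.1 progression, in a subject with no IIR progression, counts as an event on the investigator's date. Its main use is DOR, keeping the IIR responder set fixed and counting only progressions after the IIR response. The PFS version is a supplement, because it largely overlaps investigator-read PFS.

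No change to scanning or treatment is involved. The cost is SAP wording, one table and two Kaplan-Meier runs on data the plan already collects. The sensitivity estimates will probably look slightly less favourable, and they count progressions the independent reader did not call, so they should be presented as a bound beside the main result and not as a replacement.
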